2. STUDY OBJECTIVES

2.1 Primary Objective

The primary objective of this study is to evaluate the efficacy of 0.005%, 0.002%, and 0.0008% estriol vaginal gel and to determine the minimal effective dose for the treatment of postmenopausal vaginal atrophy in women that refer moderate to severe vaginal dryness as the most bothersome symptom.

2.2 Secondary Objectives

The secondary objectives of this study are to:

- Evaluate the efficacy of the three formulations of estriol vaginal gel in the improvement of other symptoms and signs of vulvovaginal atrophy.
- Evaluate the safety and tolerability of the three formulations of estriol vaginal gel.

2.3 Exploratory Objectives

The exploratory objectives of this study are to:

- Evaluate the final subjective global perception of efficacy of the three formulations of estriol vaginal gel.
- Evaluate the subject's acceptability of the three formulations of estriol vaginal gel.

3. STUDY DESIGN

This study is a double-blind, randomized, dose-ranging, placebo-controlled multicenter study with four parallel groups. Approximately 25 sites in five European countries (Czech Republic, Hungary, Italy, Spain and Sweden) will be included in the study. The study setting will include academic hospitals and gynecological clinics. The study population is postmenopausal women who report moderate to severe vaginal dryness as their most bothersome symptom in addition to other symptoms and/or signs of postmenopausal vulvovaginal atrophy.

After providing informed consent, potential subjects will be evaluated during the screening period (maximum 30 days) to determine if they are eligible to participate in the study. A screening identification number will be assigned to each eligible subject according to their order of arrival into the study at the Screening visit. Subjects who meet all of the inclusion criteria and none of the exclusion criteria (see Sections 4.1.1 and 4.1.2 of the study protocol) will be randomized into the study at the Baseline visit. A total of 280 subjects will be enrolled and randomly allocated to one of the four treatment groups (0.005%, 0.002%, or 0.0008% estriol vaginal gel or placebo vaginal gel); the allocation to treatment group will be 1:1:1:1. A blocked randomization across the entire study (i.e. all sites as a whole) will be used. Subjects will be assigned a randomization code according to their order of arrival into the study at the Baseline Visit. Initial treatment consists of daily vaginal administration of 1 gram of randomly-assigned estriol gel or placebo gel using the supplied applicator. Placebo gel will be identical in appearance, texture and odor to the estriol vaginal gel products. After 21 days of daily administration, treatment will continue with twice-weekly administration up to Week 12 (i.e., Mondays and Thursdays).

An Interactive Web Response System (IWRS) will be used in the study to assign subjects a subject number, a randomization code, to screen fail a subject, to assign drug (following randomization) at the Baseline, Week 3 and Week 8 visits, to confirm a subject has completed the study and to withdraw/discontinue a subject from the study. Subjects will be assigned a subject number during the Screening visit after the subject has provided a signed Informed Consent. The subject number will remain the same for a subject throughout the duration of the study. Subject numbers will be different from the actual randomization codes. Screen failures (subjects not randomized into the study) may be re-screened in cases where the unmet selection criteria have been resolved. A new signed Informed Consent will be needed for re-screened subjects. The subject number assigned at screening will be modified to include the number of re-screenings completed for the individual. For example, if subject 8880001 is re-screened for the first time,

they will be assigned the subject number 8881001; if re-screened for a second time, they will be assigned subject number 8882001. Only invasive procedures (endometrial biopsy and Factor V Leiden) will not be repeated if subjects are re-screened within one month the previous failure. Randomized subjects prematurely withdrawn from the study will not be replaced.

The randomization list will be kept strictly confidential, accessible only to authorized personnel until the time of unblinding. The randomization codes will be unblinded and made available for the project statistician to perform the data analysis when the study has been finalized, the database has been verified, and all protocol violations have been determined. All personnel involved directly in the study shall be unaware of the treatment assigned to the subjects until the database has been closed.

The duration of trial participation for each subject is expected to be approximately 20 weeks (from Screening to End-of-Study phone call) although the time on study treatment will be approximately 12 weeks. Subject completion is defined as the completion of all phases of the study, including the End-of-Study phone call to be performed for safety purposes at Week 16.

An overview of the study visits and procedures is given in the Schedule of Events (**Table 1 in Section 4**). Details of specific procedures are provided in **Section 4**.

4. SCHEDULE OF ASSESSMENTS

4.1 Study Visits

4.1.1 Screening Visit

Screening is defined as the period prior to the administration of study treatment. In this study, the Screening period will cover a maximum of 30 days before randomization on the day of the Baseline visit.

A subject will enter the Screening period if basic study criteria are matched with the potential participant's medical condition and profile. In case of agreement to participate, the subject will be requested to sign an Informed Consent Form (ICF).

During the Screening visit, the following procedures will be conducted for each subject. Further details are provided in Section 6.1.1 of the study protocol.

- Register the subject in IWRS to obtain unique subject identifier.
- Record demographic details: Year of birth, age and race.
- Record recent (within the past year) and relevant gynecological, medical and surgical history and any chronic or ongoing medical conditions for which the subject received or is receiving medical treatment.

- Record use of prohibited medications during the periods defined in the exclusion criteria (see Appendices 12.3 and 12.4 of the study protocol).
- Record prior (including the 4 weeks prior to study entry) and concomitant medications taken or being taken.
- Perform physical examination: General appearance; Head, eyes, ears, nose and throat (HEENT); Cardiovascular; Respiratory; Gastrointestinal; Dermatological; Neurological; Musculoskeletal; Lymphatic and any 'Other' body systems, noting any abnormal findings.
- Measurement of vital signs:
 - Height and weight
 - Seated for at least 5 minutes: blood pressure and heart rate
- Perform two 12-lead electrocardiogram (ECG) examinations, approximately 5 minutes apart from one another.
- Perform gynecological examination:
 - Visual inspection of external genitalia
 - Speculum examination of vagina
 - Speculum examination of cervix (if present)
 - Bimanual palpation of uterus and ovaries (if present)
 - Breast palpation
 - Collection of papanicolau smear
- Perform mammogram, if documented negative mammogram within 9 months prior to randomization is not available.
- Evaluation of presence and intensity of the symptom vaginal dryness.
- Collection of vaginal smear for evaluation of vaginal cytology: 2 smears to be taken, from the bottom of the right and left vaginal walls respectively.
- Collection of vaginal pH
- Perform transvaginal ultrasound (in subjects with a uterus): Endometrial thickness; Pelvic pathology.
- Perform endometrial biopsy (in subjects with a uterus).
- Collection of safety laboratory parameters: blood chemistry and hematology, including coagulation and lipids, urinalysis and serum hormone levels. These samples should be

performed under fasting conditions. A Factor V Leiden sample will also be taken at Screening if the requisite informed consent is obtained.

- Record AEs.

Before the Baseline visit, the investigator will confirm that the subject meets all the inclusion and exclusion criteria, including the endometrial histological assessment.

Subjects with signs and symptoms suggestive of infection of the genital or urinary tract requiring treatment at the start of the study will be excluded. However, once treated, the symptoms have resolved (or there are negative microbiology findings) and the required wash out period has passed according to the treatment used, subjects can be re-screened into the study. Refer to Section 4.2.3 of the study protocol for more details.

4.1.2 Baseline Visit

The Baseline visit will be performed on Day 1. The following procedures will be conducted for each subject. Further details are provided in Section 6.1.2 of the study protocol.

- Randomization: IWRS will be used to allocate the subject's randomization number and 3 study medication kit numbers.
- Evaluation of presence and intensity of the symptoms (other than vaginal dryness) and signs of vulvovaginal atrophy.
- Record AEs since the Screening visit.
- Record concomitant medications.
- Administration of the first dose of study treatment, either by the investigator or by the subject in the presence of the investigator.
- Dispensing of dosing instructions and adequate medication supplies for 3 weeks: three medication kits each containing one 10g tube of gel and 10 single-use applicators, to cover 21 expected daily applications between the Baseline visit and the Week 3 visit.
- Perform endometrial biopsy (only if the subject presents with vaginal bleeding).

4.1.3 Week 3 Visit

The Week 3 visit will be scheduled on the day after having completed 21 days of study treatment. For organizational reasons, a deviation of 3 days before or after the scheduled date is allowed.

The following procedures will be conducted for each subject. Further details are provided in Section 6.1.3 of the study protocol.

- Evaluation of presence and intensity of symptoms (including vaginal dryness) and signs of vulvovaginal atrophy.
- Collection of vaginal pH
- Collection of vaginal smear for evaluation of vaginal cytology: two smears to be taken, from the bottom of the right and left vaginal walls respectively.
- Record AEs.
- Record concomitant medications.
- Reconciliation of returned medication.
- Dispensing of adequate medication supplies: two medication kits, to cover 10 expected twice-weekly applications between the Week 3 visit and the Week 8 visit. IWRS will be used to allocate two study medication kit numbers.
- Perform endometrial biopsy (only if the subject presents with vaginal bleeding).

4.1.4 Week 8 Visit

The Week 8 visit will be scheduled on the day after having completed 8 weeks of study participation. For organizational reasons, a deviation of 5 days before or after the scheduled visit date is allowed. The following procedures will be conducted for each subject. Further details are provided in Section 6.1.4 of the study protocol.

- Record AEs.
- Record concomitant medications.
- Reconciliation of returned medication.
- Dispensing of adequate medication supplies: two medication kits, to cover eight expected twice-weekly applications between the Week 8 visit and the Week 12 visit. IWRS will be used to allocate 2 study medication kit numbers.
- Perform endometrial biopsy (only if the subject presents with vaginal bleeding).

4.1.5 Week 12 / Early Termination Visit

The Week 12 visit will be scheduled on the day after having completed 12 weeks of study participation, (or earlier if the subject terminates study participation before Week 12, in which case this status should be registered in IWRS). For organizational reasons, a deviation of 5 days before or after the estimated ideal date is allowed. The following procedures will be conducted for each subject. Further details are provided in Section 6.1.5 of the study protocol.

- Evaluation of presence and intensity of symptoms (including vaginal dryness) and signs of vulvovaginal atrophy.
- Collection of vaginal pH
- Collection of vaginal smear for evaluation of vaginal cytology: two smears to be taken, from the bottom of the right and left vaginal walls respectively.
- Evaluation of global efficacy.
- Evaluation of acceptability.
- Perform transvaginal ultrasound (in subjects with a uterus): Endometrial thickness; Pelvic pathology.
- Perform endometrial biopsy (in subjects with a uterus).
- Collection of safety laboratory parameters: blood chemistry and hematology, including coagulation and lipids, urinalysis and serum hormone levels. These samples should be performed under fasting conditions. A Factor V Leiden sample will also be taken at the Week 12 / Early Termination visit if not already obtained at Screening.
- Record AEs.
- Measurement of vital signs:
 - Weight
 - Seated for at least 5 minutes: blood pressure and heart rate
- Physical examination: General appearance; Head, eyes, ears, nose and throat; Cardiovascular; Respiratory; Gastrointestinal; Dermatological; Neurological; Musculoskeletal; Lymphatic and any 'Other' body systems, noting any abnormal findings.
- Perform two 12-lead electrocardiogram (ECG) examinations, approximately 5 minutes apart from one another.
- Perform gynecological examination:

- Visual inspection of external genitalia
- Speculum examination of vagina
- Speculum examination of cervix (if present)
- Bimanual palpation of uterus and ovaries (if present)
- Breast palpation
- Record concomitant medications.
- Reconciliation of returned medication.

4.1.6 Week 16 – End of Study Phone Call

All subjects who complete the full 12 weeks of study treatment will have a phone call scheduled for 4 weeks after the last dose of study treatment to record any AEs that may have appeared after treatment discontinuation, and to document changes in concomitant medication use. For organizational reasons, a deviation of 5 days before or after the estimated ideal date is allowed.

When a subject has completed the study, the completed status should be registered in IWRS.

An overview of the study visits and procedures is given in the Schedule of Events (**Table 1**).

Table 1: Schedule of Events

Procedure	Screening Visit	Baseline	Week 3	Week 8	Week 12 / Early Termination	Week 16 / End of Study Phone Call
Visit Window (days)	-30 to -1	1	21 ± 3	56 ± 5	84 ± 5	112 ± 5
Informed consent	X		X			
Randomization						
Medical history, medication history and demographics	X					
Physical examination ^a	X					
12-lead electrocardiogram ^b	X					
Gynecological examination ^c	X					
Transvaginal ultrasound (women who have a uterus)	X					
Mammogram (if no negative mammogram documented within 9 months prior to randomization) ^d						
Clinical laboratory tests ^e	X					
Endometrial biopsy (women who have a uterus)	X	*	*	*	X	
Adverse event reporting ^f	X	X	X	X	X	X
Concomitant medication reporting ^g	X	X	X	X	X	X
Evaluation of vaginal dryness ^g	X	X	X	X	X	X
Evaluation of symptoms and signs of vulvovaginal atrophy ^{g,h}		X	X	X	X	X
Vaginal pH	X		X		X	
Vaginal smear for evaluation of vaginal cytology	X		X		X	
Evaluation of global efficacy ⁱ					X	
Evaluation of acceptability ^j					X	
Administration of the first dose of the study medication ^k			X			
Study medication supply and dispensing ^l			X	X	X	X
Reconciliation of returned study medication			X	X	X	X

^a Physical examination to include vital signs measurements (height [Screening visit only], weight, blood pressure and heart rate).

^b Two ECG exams will be performed in each of these two visits, approximately 5 minutes apart from one another.

^c Gynecological examination to include visual inspection of external genitalia, speculum examination of vagina and cervix (if present), bimanual palpation of uterus and ovaries (if present) and breast palpation. Papanicolaou examination will be performed at the Screening visit only.

CONFIDENTIAL

Final 1.0: 22 Jun 2017

Procedure	Screening Visit	Baseline	Week 3	Week 8	Week 12 / Early Termination	Week 16 / End of Study Phone Call
Visit Window (days)	-30 to -1	1	21 ± 3	56 ± 5	84 ± 5	112 ± 5
d	Neither mammograms performed as study specific procedure nor negative mammogram documented within 9 months prior to randomization will be recorded in the eCRF but archived in subject's clinical records.					
e	Laboratory testing performed under fasting conditions at Screening and Week 12 includes: standard hematology panel plus prothrombin time, activated thromboplastin partial time, fibrinogen, antithrombin III/protein S; standard chemistry panel (glucose, cholesterol, high-density lipoprotein, low-density lipoprotein, triglycerides albumin, alanine aminotransferase, aspartate aminotransferase, creatine phosphokinase, bilirubin, creatinine, total protein, uric acid, blood urea nitrogen); hormones (estradiol, estradiol, estrone, follicle-stimulating hormone, luteinizing hormone), and standard urinalysis with microbiology. F actor V Leiden testing will be performed only at the Screening visit (or at the Week 12 / Early Termination visit if not obtained at Screening).					
f	AEs and SAEs will be recorded from Screening (post ICF signature) and subsequently at every study visit and up to 30 days post last study treatment administration.					
g	Tolerability of study treatment will be evaluated at Week 3, Week 8, Week 12 and Week 16.					
h	For the evaluation of symptoms and signs, each symptom and each sign will be graded as: 0 = Absent; 1 = Mild; 2 = Moderate; 3 = Severe.					
i	Signs and symptoms other than vaginal dryness to be evaluated are the following:					
j	Symptoms: dyspareunia; pruritus or itching; burning; dysuria.					
k	Signs: pallor; friability; thinning or flattening of folds; presence of petechiae; dry mucosa.					
l	Global efficacy will be assessed as: highly efficacious; efficacious; non-efficacious; detrimental.					
m	Global acceptability will be assessed as: excellent; good; acceptable; unacceptable.					
n	The investigator will administer the first study medication or will supervise the subject doing the administration.					
o	Medication kits will be allocated via IWRS.					
*	Endometrial biopsy is mandatory in subjects with a uterus at the Screening and Week 12 visits, and whenever the subject presents with vaginal bleeding at other visits.					

5. ANALYSIS POPULATIONS

A total of three populations will be used for all summaries and analyses. Subjects who have satisfied the population criteria will be classified in the designated population and will only be included in analyses for which they have available data.

5.1 Intent-to-Treat (ITT) Population

The ITT population is defined as all randomized subjects. The ITT population will be used to present all efficacy analyses, including the four co-primary efficacy endpoints. Subjects will be summarized according to the treatment to which they were randomized.

5.2 Per Protocol (PP) Population

The PP population is defined as all randomized subjects who complete the study to Week 12 with no major protocol deviations impacting the co-primary efficacy analyses. The major deviations impacting the analysis are defined in more detail in **Section 6.2.2**. The PP population will be used for confirmation of efficacy analyses of interest. Subjects will be summarized according to the treatment to which they were randomized.

5.3 Safety Population

The Safety population includes all randomized subjects who administered at least one dose of study treatment. The Safety population will be used to present all safety analyses. Subjects will be summarized according to the actual treatment received. In the event that a subject is administered incorrect treatment in error, the subject will be categorized according to their randomized treatment assignment if at least one dose of the correct treatment was administered during the subject's time on treatment.

6. STATISTICAL METHODOLOGY

6.1 Statistical and Analytical Issues

6.1.1 Statistical Methods

All statistical methods will be based on the International Conference on Harmonization (ICH) E9 document "Statistical Principles for Clinical Trials".

All data will be summarized by treatment group. In addition, where appropriate, a total overall group column will be included to summarize all subjects. Where appropriate, data will be summarized by treatment group and visit.

In summary and analysis tables of continuous variables, the minimum and maximum statistics will be presented to the same number of decimal places as the original data. The mean, median, quartiles, Least Squares mean (LS mean), and 95% Confidence Interval (CI) will be presented to one more decimal place than the original data. The standard deviation (SD) and standard error (SE) will be presented to two more decimal places than the original data. Standard descriptive statistics (number of subjects with data available [n], mean, SD, median, quartiles, minimum and maximum) will be presented in summary tables. The LS mean, SE and 95% CI will be presented in the statistical analysis outputs as appropriate.

In summary tables of categorical variables, the number of non-missing observations and percentages will be presented. The denominator for each percentage will be the number of subjects within the population and treatment group of interest with non-missing responses, unless otherwise specified.

All hypothesis testing will be 1-sided unless otherwise specified and carried out at the 2.5% significance level, designed to evaluate the superiority of estriol vaginal gel versus placebo vaginal gel.

P-values will be rounded to 3 decimal places. P-values less than 0.001 will be reported in the tables as '<0.001'. P-values greater than 0.999 will be reported as '>0.999'.

Should any of the statistical methods proposed prove unsuitable during the final analysis, more appropriate methods will be used and any changes will be documented in the Clinical Study Report (CSR), including the rationale for use.

All data collected on the electronic case report form (eCRF) as well as the data from central laboratories will be presented in data listings. The subject data listings will be sorted by unique subject number, randomized treatment group and visit or visit date, as appropriate. Further sorting variables may be used if required.

The Baseline assessment is defined as the last assessment prior to first administration of study medication. This will be the last assessment from either the Screening or Baseline visits.

All statistical analysis will be performed using SAS® Version 9.3 or higher.

The statistical analysis will be conducted when all data for all subjects have been entered, cleaned and locked, at which point the study will be formally unblinded.

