6.4.8 Endometrial Biopsy

An endometrial biopsy is performed in subjects with a uterus as a mandatory procedure at the Screening and Week 12 / Early Termination visits, and whenever the subject presents with vaginal bleeding at any other visit.

The slides from the endometrial biopsies will be sent to the central laboratory, [REDACTED] for evaluation. Three independent pathologists, who will be blinded to subject, treatment assignment and to each other's evaluations, will assess the endometrial biopsies obtained at the Week 12 / Early Termination visit plus 10% of the Screening slides and all slides diagnosed with hyperplasia or cancer. The slides from the Screening visit and from any visit where the subject presents with vaginal bleeding will be assessed by only the primary pathologist.

The primary pathologist will be from [REDACTED] and the other two pathologists will be from different institutions but will travel to [REDACTED] to evaluate the endometrial biopsies.

Each pathologist will provide their evaluation according to the following categories, which are ordered from best to worst diagnosis, i.e. atypical hyperplasia (carcinoma) is the most severe diagnosis, followed by complex hyperplasia, simple hyperplasia and benign endometrium accordingly.

Table 5: Histologic Characteristics of the Endometrium

0	No tissue
1	Tissue insufficient for diagnosis
2	Atrophic
3	Inactive
4a	Weakly proliferative
4b	Active proliferative
4c	Disordered proliferative
5a	Secretory - Cyclic type
5b	Secretory - Progestational type (including stromal decidualization)
6	Menstrual type
7	Simple hyperplasia without atypia
8	Simple hyperplasia with atypia
9	Complex hyperplasia without atypia
10	Complex hyperplasia with atypia
11	Carcinoma (specify type)

For any subject, the final diagnosis will be accepted as the concurrence of two of the three pathologists. If there is no agreement among the three pathologists, the most severe pathologic diagnosis will be used as the final diagnosis. The evaluations of all three pathologists must be verified by the CRA in order to be considered for final analysis.

If hyperplasia is diagnosed by the single safety reader for a subject who has bled while on study treatment, this diagnosis will be maintained for the efficacy/safety evaluation and the slides become part of the slide set given to the two other pathologists for reading.

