The bullet points below specify how many pathologists will review the biopsy samples at each visit and how the final diagnosis of a sample will be programmatically derived at each visit.

- Screening Visit
 - Biopsy sample is mandatory.
 - Samples reviewed by Pathologist 1 only.
 - Final diagnosis = diagnosis of Pathologist 1
 - 10% of samples will also be reviewed by Pathologist 2 and Pathologist 3 **for QC purposes only**. The diagnoses of Pathologist 2 and Pathologist 3 will **not** be used in the determination of final diagnosis.

- All slides diagnosed with hyperplasia or cancer (categories 7, 8, 9, 10 or 11 from Table 5 above) by Pathologist 1 will also be reviewed by Pathologist 2 and Pathologist 3 **for QC purposes only**. The diagnoses of Pathologist 2 and Pathologist 3 will **not** be used in the determination of final diagnosis.
- Baseline, Week 3 and Week 8 Visits
 - Biopsy sample is only taken if the subject presents with vaginal bleeding at the visit, otherwise the eCRF is marked as Not Applicable.
 - Samples reviewed by Pathologist 1 only.
 - Final diagnosis = diagnosis of Pathologist 1
 - All slides diagnosed with hyperplasia or cancer (categories 7, 8, 9, 10 or 11 from Table 5 above) by Pathologist 1 will also be reviewed by Pathologist 2 and Pathologist 3 **for QC purposes only**. The diagnoses of Pathologist 2 and Pathologist 3 will **not** be used in the determination of final diagnosis.
- Week 12 / Early Termination Visit
 - Biopsy sample is mandatory.
 - Samples reviewed by Pathologist 1, Pathologist 2 and Pathologist 3.
 - Final diagnosis derived as follows:
 - If the subject presents with vaginal bleeding at the visit (as indicated by an answer of 'Yes' to the direct question on the eCRF) and Pathologist 1 diagnoses hyperplasia or cancer (categories 7, 8, 9, 10 or 11 from Table 5 above):
 - Final diagnosis = diagnosis of Pathologist 1, **regardless** of the diagnoses of Pathologist 2 and Pathologist 3, even if Pathologist 2 and Pathologist 3 concur on a different diagnosis, either more or less severe than that of Pathologist 1.
 - Otherwise:
 - If two of the three pathologists agree (i.e. diagnose the same category from Table 5 above), their agreed diagnosis is the final diagnosis.
 - If all three pathologists diagnose a different category from Table 5 above), the most severe diagnosis is taken as final diagnosis.

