For summary purposes, the Baseline histologic result will be the final diagnosis from the Baseline visit if endometrial samples were taken due to the subject presenting with vaginal bleeding at that visit, or the final diagnosis from the Screening visit otherwise.

The number and percentage of subjects with each histologic characteristic will be summarized (according to the final diagnosis, as defined above) at each visit by treatment group and overall.

A table presenting the shift in result from Baseline to Week 12 / Early Termination (according to the final diagnosis) will also be presented by treatment group. For the shift table, the denominator of percentage will be the number of subjects in the Safety population in each treatment group.

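### In the by-visit endometrial histology table, women whose biopsy gave no diagnosis count in the denominator of the hyperplasia and carcinoma rows, and the shift table dilutes further

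*SAP*

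**What the plan says.** The general rule in SAP 6.1.1 is: "The denominator for each percentage will be the number of subjects within the population and treatment group of interest with non-missing responses". It allows for exceptions where the SAP states them, and it does not mention biopsies.

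The biopsy rules are in SAP 6.4.8. Table 5 there is introduced with "Each pathologist will provide their evaluation according to the following categories, which are ordered from best to worst diagnosis". It runs from code 0 (no tissue) and code 1 ("Tissue insufficient for diagnosis") through the benign categories to hyperplasia (7 to 10) and carcinoma (11). At Week 12 / Early Termination, outside the special rule for women who present with bleeding, "If two of the three pathologists agree (i.e. diagnose the same category from Table 5 above), their agreed diagnosis is the final diagnosis". That covers every Table 5 category, so 0 and 1 can be final results.

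Two outputs follow. For the by-visit table: "The number and percentage of subjects with each histologic characteristic will be summarized (according to the final diagnosis, as defined above) at each visit". No denominator is given. For the shift table: "For the shift table, the denominator of percentage will be the number of subjects in the Safety population in each treatment group".

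Protocol 7.4 names the safety endpoint as the Week 12 change in endometrial histology in women with an intact uterus. Protocol 6.3.3 has the investigator record whether tissue was obtained and send what was obtained, so failed sampling is foreseen. Neither document gives an expected failure rate or defines an evaluable biopsy.

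**The concern.** A biopsy coded 0 or 1 carries no information on whether hyperplasia is present. Such a woman can never enter the numerator for codes 7 to 11, yet the default rule leaves her in the denominator, because a code from a pathologist is a non-missing response. The printed percentages for the rows that matter most for an estrogen product can therefore only be too low as a description of women whose endometrium was actually read.

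The shift table has the same problem in a stronger form. Its denominator also takes in women without a uterus and women with no Week 12 biopsy, although the endpoint is defined for women with a uterus. The two tables would then print different percentages for the same case, and neither would be the percentage among women with a diagnosis.

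**Working it through.** **Inputs.** The default denominator comes from SAP 6.1.1; the codes, final-diagnosis rule and shift-table denominator from SAP 6.4.8; the arm size from SAP 6.1.4. The share q of biopsy results with final code 0 or 1 is not in the documents, and neither is the share of women with a uterus. Both are assumed below.

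**Step 1: the plan's arm size.** 57 / (1 - 0.18) = 69.5, rounded up to 70 per arm, and 4 × 70 = 280. Both agree with the plan. For biopsies 70 is an upper limit, because only women with a uterus are sampled.

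**Step 2: which denominator applies.** SAP 6.4.8 states an exception for the shift table and none for the by-visit table, so the default governs the latter. Codes 0 and 1 are pathologist evaluations, not missing-value codes. The only grouping made in that section is "All slides diagnosed with hyperplasia or cancer (categories 7, 8, 9, 10 or 11 from Table 5 above) by Pathologist 1", which serves the reader rules and does not define an evaluable set.

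**Step 3: size in the by-visit table.** Let N be the women with a biopsy result and x the cases in a row.

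- SAP as written: x / N
- Among diagnosed biopsies: x / [N(1 - q)]
- Ratio of the first to the second: 1 - q

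With N = 70 and x = 1, the SAP rule gives 1/70 = 1.43% whatever q is.

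| Assumed q | Diagnosed biopsies | Percentage among them |
|---|---|---|
| 0% | 70 | 1.43% |
| 10% | 63 | 1.59% |
| 20% | 56 | 1.79% |
| 30% | 49 | 2.04% |
| 50% | 35 | 2.86% |

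**Step 4: the shift table.** Assume 70 women in the Safety population of an arm, 50 of them with a biopsy result, and q = 20%, so 40 are diagnosed. For simplicity, ignore baseline failures. One case is then:

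- shift-table rule: 1/70 = 1.43%
- default rule: 1/50 = 2.00%
- diagnosed biopsies: 1/40 = 2.50%

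**The case against.** Much can be said for leaving the by-visit table alone. It is descriptive. Codes 0 and 1 get their own rows, so a reader can subtract them and recompute, and biopsy results are also listed subject by subject (Listing 16.2.10). A single case is visible as a count under any denominator. A percentage limited to diagnosed biopsies is itself conditional on a post-randomization outcome, so it is not automatically the better comparison between arms. All of this stands and keeps the point small. It does not explain why the printed percentages should include women with no diagnosis, and it does not cover the shift table.

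Some stronger readings are tempting but are not supported:

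- That an arm-level hyperplasia rate, or a confidence bound on it, is understated. Neither is planned; SAP 6.4.8 has only category percentages and shifts.
- That failed biopsies are hidden or counted as benign. They head a list said to run from best to worst, but they remain separate categories.
- That the comparison between arms is biased because estrogen changes tissue yield. Nothing in either document bears on this.
- That every failed biopsy enters the denominator. If the site obtains nothing and sends nothing, there may be no pathologist code; the result would then be missing and already excluded. The SAP does not say how the site record maps to code 0.
- That no other rule exists anywhere. A denominator footnote could sit in the Appendix I shells, so the finding is limited to the SAP body.

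**Conclusion.** The point holds as a minor one. On the SAP body as written, each percentage for codes 7 to 11 in Table 14.3.6.1 is the evaluable-biopsy percentage times (1 - q). For one case in 70 results that means 1.4% printed against 1.6% at q = 10% or 2.0% at q = 30%. These q values are assumptions, and the effect is nil if no final code is 0 or 1. Table 14.3.6.2 dilutes further, by an amount that also depends on how many women have no uterus or no Week 12 biopsy. No test, significance level, stated precision or individual diagnosis is affected. The case for acting is that the percentages describe a named safety endpoint and the correction is cheap.

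**What to change.** In SAP 6.4.8 and the shells for both tables:

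- **By-visit table (14.3.6.1).** Keep codes 0 and 1 as counts, with percentages of women biopsied. Compute percentages for codes 2 to 11 among women with a final code in that range at the visit. Add a combined hyperplasia line (7 to 10) alongside carcinoma (11).
- **Mapping.** State that a site record of no tissue is coded 0, so that all failed samples are handled alike.
- **Shift table (14.3.6.2).** Replace the Safety-population denominator with women who have a final code 2 to 11 at both Baseline and Week 12 / Early Termination.

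The cost is a few sentences and a change to two shells, with no new data, and it can be settled before unblinding. The denominators become smaller and the percentages become conditional on an evaluable biopsy, so the number of non-evaluable biopsies per arm must appear beside them. A Week 12 case in a woman with no evaluable Baseline biopsy would leave the shift table, but would still be counted in the by-visit table.
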